## **Title: Effects of Septorhinoplasty on Allergic Rhinitis**

**Abbreviations:** AR: allergic rhinitis; DS: septal deviation; VAS: visual analogue scale; RNMa: anterior rhinomanometry; QoL: quality of life; ADL: Basic activities of daily life.

**Introduction:** Allergic rhinitis (AR) is a chronic inflammatory disease that affects almost 30% of adult population and is associated to other inflammatory disease (1). In AR, upper airway respiratory mucosa is inflamed in response to allergen exposition, mediated by Th2 immunology response. Common symptoms are sneezing, rhinorrhoea, nasal congestion, nasal itching and nasal obstruction. Nasal obstruction is the most refractory symptom to medical treatment (2). AR evolution includes chronic rhinosinusitis, nasal poliposis or chronic rhinitis (3). Despite its prevalence and the variety of medication to treat AR, many patients still feel failure treatment (4). Many studies have demonstrated how AR impairs life quality and work productivity, since it is an important cause of absence from work and school, and generates huge costs in prescription medication (5).

Nasal septum deviation (DS) causes symptoms as nasal obstruction, epistaxis, snoring, anxiety, headaches, buccal breathing and sinusitis (6, 7). Septorhinoplasty (STP) is the most common treatment for patients with DS with generally satisfactory outcomes (8). AR treatment include a great variety of medication as antihistamines, anti-leukotrienes, corticoids or specific allergen immunotherapy. This conservative method implies improvement's symptoms but in some refractory patients' medication alone is not enough. Surgical procedures to treat AR includes cryotherapy, laser cauterity, sinus surgery or turbinate resection. AR guides do not include nowadays STP as therapeutic possibility, as its outcomes do not resulted as satisfactory as in patients that only show DS (9).

Some authors as Youn HyoKim et al. (2011) studied in two different AR groups how STP and turbinoplasty or turbionplasty alone affected to patient's evolution disease (10). In this study they observed a medication reduction in both groups and better scores in VAS (visual analogue scale), although there was no airflow measurement.

Current guides of AR underscore the necessity of research regarding the role of STP in the treatment of AR (11).

Our main objective is to evaluate

## **Material and methods: Patients**

**Study Design:** This will be a prospective quasi experimental non-randomized controlled pre and post-test study. Informed consent (see page 5) will be obtained from all patients in accordance with the Declaration of Helsinki of 1975, revised in 2013. This study has been approved by the Regional Research Ethics Committee of Galicia (Ref: 2015/280). Patients will be recruited in January 2021 and operated in Allergology and Otorhinolaryngology service in CHUAC (A Coruña University Hospital) in January 2021.

**Inclusion criteria:** patients aged 18-65, diagnosed with AR and DS, will be recruited. DS will be determined by rhinoscopy findings. AR diagnosis will be established clinically (history and physical examination) and testing for specific allergen sensitization (positivity > 3 mm). Studied allergen will be pollen, dust mite and fungi. Symptoms of AR should have at least 1 year evolution. AR Classification will be performed according to Aria 2008 (12), as “Intermittent AR” (less than 4 days per week symptoms) and “Permanent AR” (more than 4 days per week symptoms).

Patients with none of these symptoms will be recorded as mild nasal obstruction: sleeping disorders, daily activity impairment, absence with work or school. If the patient had any of those symptoms were classified as moderate-severe nasal obstruction.

**Exclusion criteria:** Patients with less than 1-year AR symptoms, patients treated with specific immunotherapy against allergen, patients undergoing simultaneous surgical procedure (e.g. turbinate reduction), smokers, chronic obstructive pulmonary disease, psychiatric disorders, malignant tumours, severe hepatopathy, obstructive sleep apnoea, previous nasal surgery.

[figure not shown]
**Intervention:** patients will be screened and surgical procedure will be performed by the same surgeon. Variables will be collected from clinical history before and one month after surgery.

After screening, patient's obstruction will be evaluated by anterior rhinomanometry (aRNM) ( $\text{cm}^3/\text{s}$ ) with Rhinospir Pro-165 Sibelmed® (Barcelona, Spain). Classification from mild, moderate, severe or very severe will be determined according to Rhinomanometric grading.

Quality of life (QoF) will be scored through ESPRINT scale. ESPRINT is a validated Spanish questionnaire about daily life activity, sleep, psychology and affection's perception in AR patients (13).

Symptoms like sneezing, itchy nose, ocular symptoms and nasal obstruction will be evaluated with visual analogue scale (VAS) and clinical history. VAS score will be classified as mild (1-3), moderate (4-6) and severe (7-10).

Medication (intranasal corticosteroid, ant leukotrienes, antihistamine eye drops, antihistamine) and its frequency (less than 2 intakes per week or more than 2 intakes per week) will also be registered.

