## Statistical analysis Plan

Sample size justification: If we estimate in relation to the response variable "severity" that 60% of the patients before the intervention present moderate-severe rhinitis and this percentage is expected to be reduced to 30% after 12 months, 51 patients would be needed to detect this difference as statistically significant with 95% certainty, a statistical power of 80% before a bilateral approach of paired data.

All data will be collected in a data base and analysed with SPSS version 20.0 (SPSS Inc. Chicago, Illinois).

Deviation (SD) or interquartile range will be used to describe quantitative variables. For categorical variables, the frequency and percentage will be used. Sample normality will be assessed using the Kolmogorov-Smirnov test. The univariate analysis will be used for comparing measures, either the Student's t-distribution or the Mann Whitney U test depending on the application conditions; for comparing proportions, the chi-squared test or Fisher's exact test will be used. A correlation study will be carried out between quantitative variables using the Fisher or Spearman's statistical test, according to the application conditions. Significance will be set at  $p < 0.05$ .

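### The sample size of 51 assumes a severity change at 12 months, but the only post-operative assessment the readable plan describes is at one month

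*Combined protocol and SAP*

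**What the plan says.** - **Collection times** (Material and methods, Intervention): "Variables will be collected from clinical history before and one month after surgery". The rhinomanometry, ESPRINT, VAS and medication paragraphs give no separate post-operative time.
- **Sample size** (Statistical analysis Plan): the response variable is severity. Sixty per cent of patients are assumed to have moderate-severe rhinitis before the intervention, and "this percentage is expected to be reduced to 30% after 12 months". On that basis "51 patients would be needed to detect this difference as statistically significant with 95% certainty", with 80% power and a two-sided paired comparison. No source is cited for the 30%.
- **Severity**: the inclusion criteria split patients into mild and moderate-severe by whether sleep, daily activity or attendance at work or school is affected: "If the patient had any of those symptoms were classified as moderate-severe nasal obstruction". This is the most plausible meaning of severity in the sample size sentence, but the plan does not say so. A four-level rhinomanometric grade ("Classification from mild, moderate, severe or very severe will be determined according to Rhinomanometric grading") and a three-level VAS grade are also defined.
- **Calendar**: "Patients will be recruited in January 2021 and operated in Allergology and Otorhinolaryngology service".

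The only other one-year period in the text is the minimum duration of allergic rhinitis symptoms at entry, which is not a follow-up time.

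**The concern.** In a before-and-after study the post-operative time is part of the definition of the effect. A change one month after nasal surgery and a change at 12 months are different claims, and the plan attaches its only power statement to the one it does not schedule.

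Two things are at stake. If 12 months is intended and staff follow the schedule as written, the outcome that sized the study is never collected. If one month is intended, the plan gives no expected rate at that time, so neither the 51 nor the 80% is justified for the comparison that will be made. In both cases the reader cannot tell which time the severity conclusion will apply to.

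**Working it through.** **Inputs from the sample size justification:** 60% before, 30% after, two-sided 5%, 80% power, paired data, 51 patients. The plan gives no correlation between the two times, no discordant proportion and no allowance for losses.

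**Step 1. Reproduce 51.** Assume the before and after states are independent. The discordant cells are then

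- improved: 0.60 × 0.70 = 0.42
- worsened: 0.40 × 0.30 = 0.12
- total s = 0.54, difference d = 0.42 − 0.12 = 0.30

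McNemar, normal approximation:

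n = [1.960·√s + 0.842·√(s − d²)]² / d² = [1.960·√0.54 + 0.842·√0.45]² / 0.09 = 44.7

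With continuity correction:

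(n/4)·[1 + √(1 + 4/(n·d))]² = (44.7/4)·[1 + √(1 + 4/(44.7 × 0.30))]² = 51.1

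The exact two-sided McNemar test gives power 79.4% at 49 pairs, 80.3% at 50 and 81.2% at 51. The stated 51 is therefore reproduced to within two patients. Time does not enter the formula. It enters only through the assumed after-rate.

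**Step 2. Vary the one-month rate.** The documents give none, so the rates below are assumptions. Let phi be the correlation between a patient's before and after states. With baseline 0.60 and after-rate q:

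- P(moderate-severe at both times) = 0.60q + phi·√[0.60 × 0.40 × q(1 − q)]
- improved = 0.60 minus that; worsened = q minus that

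Power is the exact conditional McNemar power, averaged over the number of discordant pairs. Required n is the smallest at which power is at least 80% for that n and the next five.

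| Assumed one-month rate | Power, 51 pairs, phi = 0 | Power, 51 pairs, phi = 0.3 | Pairs for 80%, phi = 0 | Pairs for 80%, phi = 0.3 |
|---|---|---|---|---|
| 25% | 93% | 99% | 36 | 27 |
| 30% | 81% | 94% | 50 | 36 |
| 35% | 64% | 81% | 71 | 51 |
| 40% | 43% | 59% | 107 | 79 |

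Fifty-one pairs keep about 80% power up to a one-month rate of roughly 30% (phi = 0), 35% (phi = 0.3) or 39% (phi = 0.5).

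**Step 3. If 12 months is meant and 60% to 30% holds.** Losses before 12 months then matter:

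| Complete pairs | Power, phi = 0 | Power, phi = 0.3 |
|---|---|---|
| 51 | 81% | 94% |
| 46 | 76% | 91% |
| 41 | 71% | 87% |

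Under independence 80% needs 50 pairs, so only 51 − 50 = 1 loss can be absorbed. At phi = 0.3 it needs 36, so 51 − 36 = 15 losses can be.

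**Which test.** McNemar is used because the sample size sentence specifies paired data. The analysis text says that "for comparing proportions, the chi-squared test or Fisher's exact test will be used", so these figures are not the powers of the tests it names.

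**The case against.** - **Gaps in the file.** A figure just before the Intervention paragraph is not shown, and the statement of the main objective breaks off. Either could name a 12-month visit. This stands as a limit: such a visit cannot be ruled out. It does not remove the conflict, because the sentence naming one month would still have to be amended.
- **The one-month sentence covers only variables from the clinical history.** It may not govern rhinomanometry, ESPRINT or VAS. But the mild versus moderate-severe split rests on sleep, daily activity and absence, which are history items, and no measure has any other post-operative time.
- **Power may be unaffected.** If 30% is also reasonable at one month, 51 stands. This is correct, and no loss of power is claimed. The lack of a source for the 30% is a weakness at either time, whatever the conflict.
- **The less favourable figures depend on independence.** This is also correct. Repeated states in the same patient may well be correlated. At phi = 0.3 a one-month rate of 35% still needs only 51 pairs, and the uncorrected formula in Step 1 gives 45 rather than 50 at 30%.
- **It may be a one-phrase slip.** Possibly, but the text does not show which section is wrong, and the answer changes the follow-up, the effect of losses and the permitted conclusion.

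**Conclusion.** The concern holds and must be fixed. The study is sized on a severity change at 12 months, while the only post-operative collection time in the readable text is one month. That contradiction is explicit and does not depend on any calculation, nor on which severity scale is meant, since none is given a 12-month time.

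The size of the consequence is conditional. The 80% is unsupported at one month but not shown to be lost: across assumed one-month rates of 25% to 40%, power with 51 pairs runs from 93% down to 43% under independence and from 99% down to 59% at phi = 0.3. The rates, correlations and numbers of complete pairs used here are assumptions, because the documents supply only the 60%, the 30% and the 51.

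**What to change.** Reconcile the Intervention paragraph and the sample size justification to one primary outcome time, and state which classification severity refers to.

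- **If one month is intended:** replace the reference to 12 months, and state and justify the expected one-month rate. Give the power of 51 pairs at that rate, or recompute n if it falls below 80%. Limit the severity conclusion to one-month change, noting that allergen exposure then may differ from baseline (not quantified here). *Cost:* wording and one justified rate, with no new visit. The stated power may become less favourable, or n may rise; for example, a 35% rate needs 71 pairs under independence but 51 at phi = 0.3.
- **If 12 months is intended:** add the 12-month assessment, with the same instruments, to the Intervention paragraph. Cite the basis for 30%, and restate the power for the number of complete pairs expected at that time. *Cost:* one later assessment per patient and a longer study.

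### The VAS is banded on an unstated scale and the SAP does not say whether score or band is analysed; analysing raw within-patient change would protect power for modest effects at almost no cost

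*Combined protocol and SAP*

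**What the plan says.** All references are to the combined protocol and SAP.

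- Material and methods, on symptoms: "Symptoms like sneezing, itchy nose, ocular symptoms and nasal obstruction will be evaluated with visual analogue scale (VAS) and clinical history". The next sentence reads "VAS score will be classified as mild (1-3), moderate (4-6) and severe (7-10". The lower end of the scale, whether scores are whole numbers, and any rounding rule are not given.
- Material and methods, on rhinomanometry: flow is measured in cm3/s, and "Classification from mild, moderate, severe or very severe will be determined according to Rhinomanometric grading". The cut-points are not printed.
- Statistical analysis Plan: "The univariate analysis will be used for comparing measures", by Student's t or Mann-Whitney U. Proportions go to chi-squared or Fisher's exact test. Neither the VAS nor rhinomanometric flow is assigned to a test.
- Statistical analysis Plan, sample size: it rests on a yes/no severity variable, 60% before surgery, and "this percentage is expected to be reduced to 30% after 12 months", in a paired two-sided comparison; "51 patients would be needed to detect this difference as statistically significant". The only rule in the plan that yields a moderate-severe class uses sleep, daily activity and absence ("If the patient had any of those symptoms were classified as moderate-severe nasal obstruction"), not the VAS.

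**The concern.** Two things are left open.

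First, the printed bands cover whole numbers from 1 to 10 and nothing else. A VAS may start at 0 and may be read to a fraction of a point; the plan does not say whether this one does. Several symptoms are scored, and a patient need not have all of them. A patient with no eye symptoms could score 0 even before surgery, and an absent symptom is the best possible result after it. Any scores left out or placed ad hoc would then fall mostly on the post-operative side of the comparison.

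Second, banding is the only handling of the VAS that the plan states, and the SAP offers tests for both measures and proportions. An analyst could follow the text and report means, three ordered bands or a proportion. The named tests treat the two visits as separate samples, or can be read that way. At stake is power on outcomes that are already recorded on a finer scale, and a choice of analysis that could be made after the data are seen.

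**Working it through.** **1. The plan's own figure.** Inputs from the SAP: 60% and 30%, two-sided 0.05, power 80%, paired. No discordant rates are given, so I assume independence between visits: p10 = 0.6 × 0.7 = 0.42, p01 = 0.4 × 0.3 = 0.12, ψ = 0.54, d = 0.30.

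McNemar: n = (1.96√ψ + 0.8416√(ψ − d²))² / d² = (1.440 + 0.565)² / 0.09 = 44.7.

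With continuity correction: (44.66/4) × (1 + √(1 + 4/(44.66 × 0.30)))² = 51.1.

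Exact McNemar power at 51 is 81.2%. The stated 51 is therefore reproduced, and no VAS band enters it.

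**2. Coverage of the bands.** On whole numbers 1 to 10 every score has a band. On whole numbers 0 to 10, only 0 has none. On a continuous scale, values between 3 and 4, between 6 and 7, and below 1 have none. With a continuous 0–10 scale, baseline mean 5.5, SD 2 to 2.5, correlation 0.3 to 0.7 and mean falls of 0.8 to 1.5 points (all assumed), about 25–30% of post-operative scores lie between bands and about 3–12% lie below 1.

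**3. What banding hides.** On whole scores 1 to 10, 7 of the 9 possible one-point falls and 4 of the 8 two-point falls stay within a band.

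**4. Power, by formula.** Assumed: 51 pairs, SD 2.3 at each visit, correlation 0.5, mean fall 1.0.

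- SD of change = 2.3 × √(2(1 − 0.5)) = 2.3, and its standard error = 2.3/√51 = 0.322. The ratio is 1/0.322 = 3.11, so power is about Φ(3.11 − 1.96) = 87%.
- Treated as two independent samples, the standard error used is 2.3 × √(2/51) = 0.455, and the ratio is 2.20. Because the data really are paired, that ratio has SD 0.322/0.455 = 0.71. Power is about Φ((2.20 − 1.96)/0.71) = 63%.

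These are normal approximations that ignore rounding and truncation of the scores.

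**5. Power, by simulation.** Same assumptions, baseline mean 5.5, scores rounded and limited to 0–10, 0 counted as mild unless removed.

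| Analysis | Fall 1.0 | Fall 1.5 | Fall 2.5 |
|---|---|---|---|
| Raw score, paired t | 84% | 99% | 100% |
| Raw score, signed-rank | 83% | 99% | 100% |
| Bands, signed-rank | 71% | 96% | 100% |
| Bands, zeros removed, signed-rank | 68% | 94% | 100% |
| Raw score, Mann-Whitney | 58% | 95% | 100% |
| Bands, chi-squared | 37% | 79% | 100% |

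Runs differed by a point or two (chi-squared at a 1-point fall gave 35% to 37%). Post-operative zeros were 4% at a fall of 1.0, 14% at 2.5 and 26% at 3.5.

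**6. Sensitivity.** On the continuous scale of step 2, where the paired t test on raw scores has about 80% power, the signed-rank test on three bands loses 11 to 22 percentage points.

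**The case against.** The plan says that scores will be classified, not that the band replaces the score. The SAP describes quantitative variables, checks normality and compares measures, and both VAS and flow fit that route. Student's t could also be read as the paired form. If the scale is whole numbers from 1 to 10, there is no gap at all. The sample size rests on another variable. The power inputs are assumed, and the assumed baseline puts about 81% of patients above mild, against the plan's 60% moderate-severe. If VAS above mild is used as a stand-in for severity, a change from 60% to 30% is a fall of about 1.8 points from a mean near 4.1. Power is then 99.9% on raw scores, 98% on bands and 94% on bands with zeros removed.

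Most of this stands. It rules out two inferences that a reader might draw: that symptom-free patients definitely cannot be classified, and that the trial as planned has lost power. The first needs a scale range that the plan does not give. The second needs the bands to be the analysed variable, which the plan permits but does not require. Nor is any gap shown in the rhinomanometric grades, since their cut-points are not in the documents. The two harms also barely coincide in this model: where zeros are common, power is near 100%, and where power is lost, zeros are about 4% and removing them costs about 3 points.

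The objection does not remove the silence on scale and analysis variable, or the absence of a named paired test. Student's t is paired in the text with Mann-Whitney U, which is a test for independent groups.

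**Conclusion.** The point holds in conditional form. The VAS range and resolution are unstated, so 0 and non-integer scores, if recordable, have no band. The SAP leaves open whether score or band is analysed and names no paired test. If bands replace scores, a modest effect is harder to detect: at an assumed 1-point mean fall, power drops from about 84% to 71% with a signed-rank test on bands, or to about 37% with the chi-squared test that the SAP names for proportions. Even on raw scores, Mann-Whitney gives only 58%. At about 2.5 points none of this matters.

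The mean, SD, correlation and falls are assumptions; the documents give none. The figures show direction and rough size, not this trial's actual power. The stated 51 patients is not affected. Stating the scale and completing the bands would, alone, only supply missing detail. The real gain is in committing to raw within-patient change with a paired test.

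**What to change.** In the Statistical analysis Plan, state that VAS (each symptom) and rhinomanometric flow in cm3/s are analysed as raw within-patient change from before to after surgery, with a paired t test or, if its conditions are not met, a Wilcoxon signed-rank test. State that VAS bands and rhinomanometric grades are descriptive only.

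In Material and methods, give the VAS range and resolution and make the bands exhaustive. On a 0–10 scale, for example: 0 none, above 0 to 3 mild, above 3 to 6 moderate, above 6 to 10 severe.

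The cost is a few sentences. No new data, patients or procedures are needed, and the sample size stays at 51. The wording should be fixed before outcome data are examined.

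### Medication frequency has no class for exactly 2 intakes a week, and a reduction within a class does not show on that variable

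*Combined protocol and SAP*

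**What the plan says.** The last paragraph of Material and methods lists what is registered: "Medication (intranasal corticosteroid, ant leukotrienes, antihistamine eye drops, antihistamine) and its frequency". The frequency is given in two classes: "less than 2 intakes per week or more than 2 intakes per week". No third class, weekly count, dose or medication score is described.

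The Intervention paragraph of the same section sets the timing: "Variables will be collected from clinical history before and one month after surgery". The Statistical analysis Plan has no analysis specific to medication. Its general rule is "For categorical variables, the frequency and percentage will be used", and it gives no rule for a value that falls in no class.

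The Introduction describes an earlier surgical study in which "they observed a medication reduction in both groups and better scores in VAS".

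The inclusion criteria split the type of rhinitis in the same way, into "less than 4 days per week symptoms" and "more than 4 days per week symptoms", and refer to a published classification for it.

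**The concern.** There are two separate problems.

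- **The classes are not exhaustive.** Neither contains exactly 2. Whoever completes the form must leave such a patient blank or choose a side, and two people may choose differently. The patient may also be coded one way before surgery and the other way after it, which would create or hide a change.
- **The classes are coarse for a pre/post comparison.** A patient who goes from 7 intakes a week to 3 is in the upper class both times. On this variable nothing has happened.

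At stake is the credibility of any statement about medication use after surgery. Since the Introduction reports reduced medication in earlier work, readers will look for that result here.

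**Working it through.** The plan gives no figure to reproduce on this point. The check is whether the classes cover every value, followed by a count of patterns for illustration.

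**Inputs.** The two class definitions come from the medication paragraph. The 51 patients come from the sample size justification. The range of whole weekly intakes is my assumption: 0 to 7, then 0 to 14 (up to two a day). I also read the frequency as recorded for each drug.

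**Step 1: coverage.** The lower class (below 2) holds 0 and 1. The upper class (above 2) holds 3 and more. The value 2 is in neither.

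**Step 2: possible reductions, range 0 to 7.** There are 8 × 7 / 2 = 28 pairs with a higher value before surgery than after.

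| Type of reduction | Pairs |
|---|---|
| From 3–7 to 0–1: class changes | 5 × 2 = 10 |
| Both values in 3–7: class unchanged | 5 × 4 / 2 = 10 |
| From 1 to 0: class unchanged | 1 |
| Starts or ends at 2: cannot be classified | 2 + 5 = 7 |
| Total | 28 |

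**Step 3: allow for stopping.** If stopping shows through the registered medication, all 7 pairs ending at 0 are visible. So are the 5 pairs from 3–7 to 1. That makes 12 visible, 10 hidden (both values in 3–7) and 6 that involve an unclassified 2 (2 to 1, and 3–7 to 2).

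**Step 4: does assigning 2 to a class remove the second problem?** Stopping still counts as visible.

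- 2 in the lower class: hidden pairs are the 10 within 3–7 plus 2 to 1, so 11 of 28.
- 2 in the upper class: hidden pairs are those within 2–7, 6 × 5 / 2 = 15 of 28.
- Range 0 to 14 (15 × 14 / 2 = 105 pairs): 12 × 11 / 2 + 1 = 67 hidden, or 13 × 12 / 2 = 78 hidden.

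The reductions among values of 3 or more remain hidden whichever side 2 takes. That follows from the class definition; only the counts depend on the assumed range.

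**Step 5: weight of one patient.** 1/51 = 1.96%, or about 2.0 percentage points, if all 51 are in the denominator.

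Steps 2 to 4 count patterns that could occur. They are not patient proportions and do not measure impact.

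**The case against.** The strongest reply is that this is loose wording about a minor variable. Medication is registered in addition to the main measures, the sample size rests on severity, and no section names medication as an outcome. The statement of the main objective breaks off in the available text, so its role cannot be confirmed. Variables come from the clinical history, so the exact intake may exist in the source, and the two classes may be only a later grouping. The frequency could also be meant for medication overall, not for each drug. All of this is fair and keeps the point small. It does not supply a class for 2 or make a fall from 7 to 3 visible on the variable as described.

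Some stronger readings are tempting but not supported:

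- **That the count is certainly lost.** The documents do not say whether it is kept.
- **That the side for 2 could be chosen once results are known.** If only the class is stored, there is nothing to reassign later. The risk is blank or inconsistent entries.
- **That the pair counts show how much information is lost.** They depend on an assumed range, and the documents give no intake distribution.
- **That the VAS bands share the defect.** The bands 1–3, 4–6 and 7–10 cover every whole score from 1. A gap exists only if 0 or finer scores are allowed, and the score exists before it is banded.
- **That the split at 4 symptom days is undefined.** The wording has the same gap, but the plan refers to a cited classification that may settle it.

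The sections also disagree on follow-up, with one month in the Intervention paragraph and 12 months in the sample size justification. This point applies at either time.

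**Conclusion.** The concern holds as a minor point. As printed, exactly 2 intakes a week has no class, and a pre/post reduction within a class does not show on the frequency variable. Both follow from the wording alone. Complete stopping of a drug may still be seen.

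The number of patients affected cannot be derived from the documents. The only size that can be stated is that each patient at exactly 2 is worth about 2.0 percentage points, on the assumption that all 51 patients are analysed. The sample size is unaffected.

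**What to change.** Record the number of intakes per week for each drug, with 0 for none, before and after surgery, and compare it within patient. Counts can be grouped later, whereas classes cannot be ungrouped.

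If the two classes are kept for description, the investigators should assign exactly 2 to one of them, in writing, before data are collected. This alone would close the gap but would not make within-class reductions visible.

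Reconcile the wording at 4 symptom days in the inclusion criteria with the classification cited there, so that each value has one class.

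The cost is a few words in the plan and a small change to form coding, with no extra visits or patients.
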